# 6 Statistical Analysis

# 6.1 **Baseline Characteristics**

Baseline characteristics will be summarised and listed.

Baseline characteristics for subjects transferred to open-label treatment at Week 16 will be presented by previous treatment and overall.

Duration of AD in years will be calculated as (age at Week 0) minus (age at onset of AD).

The table of concomitant medication at baseline will include medication starting before the first dose of IMP which does not end before the first dose of IMP. For further details, see Section 6.8.3 and Section 6.8.4.

# 6.2 Disposition

Subject disposition will be summarised and listed.

# 6.3 Rescue medication

Rescue medication is defined by the following algorithm: Concomitant medications with Dermatitis atopic or Dermatitis infected as the preferred term for the indication and either ATC2 code H02 or D07, or ATC4 code D11AH or Preferred name Methotrexate, Ciclosporin, Azathioprine, Mycophenolate-mofetil, Mycophenolate-sodium, Mycophenolate-acid or Dupilumab.

According to the protocol investigators should make every attempt to conduct efficacy and safety assessments immediately before administering any rescue treatment. Therefore, if rescue medication has start date the same day as an efficacy assessment, then the assumption will be that the assessment is not influenced by the rescue medication, see also Section 6.8.4.

Rescue medication will be summarised separately for the initial and maintenance period. In addition, a summary table of rescue medication by type (topical and systemic) and by overall group (corticosteroids, immunosuppressants and other) will be made.

For subjects continuing with maintenance or open-label treatment at Week 16, the table of rescue medication during initial treatment period will include rescue medication taken (but not necessarily initiated) between the first dose of initial treatment and the first dose of either maintenance or open-label treatment. For subjects who do not continue with maintenance or open-label treatment, the table of rescue medication during initial treatment period will include medications taken after the first dose and before the (nominal) Week 16 visit (or before day 7\*16=112 after first dose, in case the (nominal) Week 16 visit did not take place).

The table of rescue medication during the maintenance treatment period will include rescue medication taken (but not necessarily initiated) after the first maintenance dose and exclude rescue medication initiated during the follow-up period.

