9.6 Prohibited medication and procedures

The following medications are prohibited during the trial from randomisation through Week 52 (or Week 68):

- TCS of any WHO class (except for subjects in open-label treatment).
- Other topical medications used for the treatment of AD, such as TCI.
- Use of ultraviolet A or B (UVA or UVB), psoralen + UVA (PUVA), other phototherapy, or tanning beds.
- Prescription emollients or emollients containing additives such as ceramide, hyaluronic acid, urea, or filaggrin (unless treatment was initiated prior to screening).
- Three or more bleach baths per week.

Any prohibited topical treatments must be recorded as concomitant medication.

The following medications are prohibited during the trial from randomisation through safety follow-up (FU1 [Week 66] or FU2 [Week 82]):

• Investigational agents other than tralokinumab

- Immunoglobulin or blood products
- Systemic corticosteroids (nasal and inhaled corticosteroids are allowed)
- Systemic treatment for AD with an immunosuppressive/ immunomodulating agent (e.g., cyclosporine, mycophenolate mofetil, azathioprine, methotrexate, Janus kinase inhibitors, interferon-gamma, or other biologics)
- Allergen immunotherapy
- Live (attenuated) vaccine

The sponsor's medical expert must be notified if a subject receives any of these medications during the trial.

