9.7 Rescue treatment

Initial treatment period and maintenance treatment period

If medically necessary (i.e., to control intolerable AD symptoms), rescue treatment for AD may be provided to trial subjects at the discretion of the investigator. For the purpose of efficacy analysis, subjects who receive rescue treatment during the initial treatment period will be considered as non-responders, but they will continue IMP treatment if rescue consisted of topical medications.

TCI may be used for rescue, but should be reserved for problem areas only, for example face, neck, intertriginous and genital areas, etc. If possible, investigators should attempt to limit the first step of rescue therapy to topical medications, and escalate to systemic medications only for subjects who do not respond adequately after at least 14 days of topical treatment.

If a subject receives rescue treatment with systemic corticosteroids or non-steroidal systemic immunosuppressive drugs (cyclosporine, methotrexate, mycophenolate mofetil, azathioprine, etc.), IMP will be immediately discontinued (see Section 9.8.2, reasons for temporary discontinuation of IMP). After the treatment with these medications is completed, IMP may be resumed if deemed appropriate by the investigator and sponsor's medical expert, but not sooner than 5 half-lives after the last dose of systemic rescue medication.

Investigators should make every attempt to conduct efficacy and safety assessments (for example disease severity scores, safety labs) immediately before administering any rescue treatment. An unscheduled visit may be used for this purpose, if necessary.

Trial ID: LP0162-1325	Date: 14-Aug-2018	Version: 4.0
		Page 60 of 169

Open-label tralokinumab arm only

From Week 16 through safety follow-up (FU1 [Week 66] or FU2 [Week 82]) subjects may use mild to moderate strength TCS and/or TCI as needed (prn usage) on lesional skin at the investigator's discretion (see Appendix 9 for TCS classification and examples). Use of TCS and TCI should be recorded as concomitant medication.

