9.8.2 Reasons for temporary discontinuation of IMP

IMP dosing may be temporarily suspended in the event of:

- Other intercurrent illnesses or major surgery.
- An infection that requires parenteral treatment with antibiotic, antifungal, antiviral, anti-parasitic, or anti-protozoal agents.
- Treatment with systemic corticosteroids or non-steroidal immunosuppressive/immunomodulating medications (e.g., cyclosporine, methotrexate, azathioprine, mycophenolate mofetil, Janus kinase inhibitors, biologic agents).

IMP dosing may resume after the medication leading to suspension of IMP is discontinued.

A decision to discontinue IMP temporarily or to reinstitute IMP treatment must be discussed with sponsor's medical expert. However, the investigator may suspend trial treatment at any time, even without consultation with sponsor's medical expert if the urgency of the situation requires immediate action and if this is determined to be in the subject's best interest. In such cases, sponsor's medical expert should be informed as soon as possible.

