12.2 Trial analysis sets

All screened subjects will be accounted for in the CTR.

Trial ID: LP0162-1325	Date: 14-Aug-2018	Version: 4.0
		Page 92 of 169

All subjects randomised to initial treatment are included in the full analysis set and will be analysed for efficacy up to Week 16 (visit 12). Exclusions from the full analysis set can be considered in special cases as described in ICH E9, Section 5.2.1, Full Analysis Set. If it is decided to exclude a randomised subject from the full analysis set, a justification addressing ICH E9 will be given.

A per protocol analysis set will be used as an efficacy subset for the analysis of the primary endpoints up to Week 16 (visit 12), and analyses based on the per protocol analysis set will be performed to support the results obtained for the full analysis set. The per protocol analysis set will be defined by excluding subjects from the full analysis set for whom any of the following conditions apply:

- Receive no treatment with the IMP.
- Provide no assessment of IGA or EASI following start of treatment.
- Are known to have taken the wrong IMP throughout the initial treatment period of the trial.
- Do not fulfil all the inclusion criteria no. 3, 6, 7 and 8.

A maintenance analysis set will be defined as all subjects who receive tralokinumab in the initial treatment period and who are re-randomised to maintenance treatment.

A safety analysis set will be defined by excluding subjects from the full analysis set who either received no treatment with IMP and/or for whom no post-baseline safety data are available.

A maintenance safety analysis set will be defined as subjects in the full analysis set who are re-randomised to maintenance treatment at Week 16 (visit 12) and who have safety data available after Week 16.

An open-label safety analysis set will be defined as subjects in the full analysis set who are still in the trial at Week 16 (visit 12), who have safety data available after Week 16 and who at any point in time enter the open-label treatment arm.

Based on the above-mentioned rules, the inclusion/exclusion of subjects from the trial analysis sets will be documented in the statistical analysis plan update before breaking the randomisation code.

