12.3.5.1.1 Primary estimand: 'composite'

The primary estimand for the primary endpoints will be:

• Treatment difference in response rates of IGA 0/1 and EASI75 after 16 weeks achieved without rescue medication, regardless of treatment discontinuation.

The primary estimand assesses the expected difference in response rates (defined as response obtained without initiation of any rescue medication) after 16 weeks, resulting from initiation of a treatment regimen with tralokinumab compared to a treatment regimen with placebo.

Primary analysis for the primary estimand

Data retrieved at Week 16 for subjects who have permanently discontinued IMP prior to Week 16 will be included in the analysis. Subjects who prior to the Week 16 visit have received rescue medication will be considered non-responders, reflecting an assumption that initiation of rescue medication indicates failure of the randomised treatment to achieve response, and that a (possible) observed positive response after initiation of rescue medication is not attributable to the randomised treatment. Missing data for subjects who did not attend the Week 16 visit and where rescue medication has not been used prior to Week 16, will be imputed as non-responders.

The difference in response rates between treatment groups will be analysed using the Cochran-Mantel-Haenszel test stratified by region (North America, Japan, and Europe) and baseline disease severity (IGA 3 or 4). The treatment estimate and the corresponding 95% CI

Trial ID: LP0162-1325	Date: 14-Aug-2018	Version: 4.0
		Page 97 of 169

will be presented. The null hypothesis of no difference in response rates between tralokinumab and placebo will be tested against the 2-sided alternative that there is a difference.

The primary endpoints will be tested sequentially at a 5% significance level. IGA 0/1 will be tested first, and, if significant, then EASI75 will be tested. If both primary null hypotheses are rejected, the secondary endpoints and the maintenance endpoints will be tested.

Sensitivity analyses for the primary estimand

Two sensitivity analyses are specified for the primary estimand. In both cases the same Cochran-Mantel-Haenszel test as used for the primary analysis will be applied including stratification by region and baseline disease severity.

The purpose of the analyses is to assess the robustness of results of the primary analysis with respect to the retrieved data at Week 16 and assumptions regarding missing Week 16 data.

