Sensitivity analysis 1: All subjects who have permanently discontinued IMP prior to Week 16 will be imputed as non-responders, even if no rescue medication has been used. This is to reflect a situation where retrieved efficacy data and concomitant medications could be registered less accurately for subjects who have discontinued treatment.

Sensitivity analysis 2: Rather than imputing all subjects who do not attend the Week 16 visit and where rescue medication has not been used as non-responders, the following approach will be applied. If subjects have withdrawn due to an AE or due to lack of efficacy, they are still considered non-responders. Data missing for other reasons will be imputed using last observation carried forward (LOCF), hereby assuming that the last value is a more reliable estimate of the missing response (than a non-response).

Supplementary analysis

The primary analysis of the primary estimand is repeated based on the per protocol analysis set.

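### Minor: SAP 6.3 defines rescue by a closed list, while protocol 9.7 leaves systemic rescue open, so an unlisted systemic agent given for atopic dermatitis might not be flagged

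*SAP*

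**What the plan says.** Protocol 12.3.5.1.1 defines the primary estimand through "response obtained without initiation of any rescue medication". Subjects who received rescue before the Week 16 visit are counted as non-responders.

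Protocol 9.7 is the section that describes rescue. It covers topical medication (including TCI for problem areas), systemic corticosteroids, and "non-steroidal systemic immunosuppressive drugs (cyclosporine, methotrexate, mycophenolate mofetil, azathioprine, etc". The last group is open: four drugs are named as examples.

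SAP 6.3 replaces this with an algorithm. A concomitant medication is rescue if its indication is coded to atopic or infected dermatitis and it also has ATC2 code H02 or D07, or ATC4 code D11AH, or "Preferred name Methotrexate, Ciclosporin, Azathioprine, Mycophenolate-mofetil, Mycophenolate-sodium, Mycophenolate-acid or Dupilumab". There is no catch-all term and no review step for unlisted agents.

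Two other protocol sections name wider classes. Section 9.6, on prohibited medication, lists as systemic treatment for the disease "cyclosporine, mycophenolate mofetil, azathioprine, methotrexate, Janus kinase inhibitors, interferon-gamma, or other biologics". Section 9.8.2, on reasons to suspend IMP temporarily, ends its list with "mycophenolate mofetil, Janus kinase inhibitors, biologic agents".

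**The concern.** The estimand speaks of any rescue, but the rule that implements it is a fixed list. The SAP names no Janus kinase inhibitor, no interferon-gamma and no biologic except dupilumab. If the three codes do not cover such agents, a subject who receives one for atopic dermatitis is not flagged and an observed response is credited to randomised treatment.

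The same flag is used in many places. It sets non-response for both primary endpoints and for the itch endpoint (protocol 12.3.5.1.1 and 12.3.5.2). It sets non-response for both maintenance endpoints and selects who enters those analyses (12.3.6.1). It decides which SCORAD and DLQI data enter their primary analysis (12.3.5.2.1) and drives their added composite estimand (SAP 6.6.3). What is at stake is that the flag matches the estimand and that reported rates are correctly classified.

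**Working it through.** **Step 1. Compare the lists.**

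| Agent | Protocol 9.7 (rescue) | Protocol 9.6 / 9.8.2 | SAP 6.3 |
|---|---|---|---|
| Ciclosporin, methotrexate, mycophenolate mofetil, azathioprine | named | named in both | named |
| Other non-steroidal systemic immunosuppressants | open-ended | open-ended in both | only if a code covers them |
| Dupilumab | not named | within the biologics class | named |
| Other biologics | not named | class named in both | only if a code covers them |
| Janus kinase inhibitors | not named | class named in both | only if a code covers them |
| TCI | named | named in 9.6 | not named, so only if a code covers it |

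The SAP rule has 3 codes and 7 names. All four systemic drugs named in 9.7 are present, so the gap is the open-ended part.

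**Step 2. Do the codes close the gap?** Neither document says what H02, D07 or D11AH contain. The SAP's own text points both ways. It names systemic agents individually beside the codes, which suggests that the codes do not carry those classes. But it names no TCI, which 9.7 allows as rescue, so the codes presumably carry some unnamed agents.

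**Step 3. Does another rule catch a missed case?**
- Sensitivity analysis 1: "All subjects who have permanently discontinued IMP prior to Week 16 will be imputed as non-responders". This covers permanent discontinuation only. Protocol 9.7 and 9.8.2 treat systemic rescue as a temporary suspension after which IMP may resume.
- Per protocol set (12.2): there are four exclusions, the last being "Do not fulfil all the inclusion criteria no. 3, 6, 7 and 8". None concerns concomitant medication.
- Section 9.6 says the sponsor's "medical expert must be notified if a subject receives any of these medications during the trial". This records the use but does not change the flag. Deviation reporting (Appendix 4D) is the same.
- Blinded review of the analyses (12.3.10): this could include the flag but does not say so.

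**Step 4. Size per case.** One reclassified subject moves an arm's rate by 100/n points, with n from protocol 12.1.

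| Analysis | n | Points per case |
|---|---|---|
| Week 16, tralokinumab | 585 | 0.17 |
| Week 16, placebo | 195 | 0.51 |
| Maintenance IGA, each active arm | 70 | 1.43 |
| Maintenance IGA, placebo | 35 | 2.86 |
| Maintenance EASI75, each active arm | 94 | 1.06 |
| Maintenance EASI75, placebo | 47 | 2.13 |

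**Step 5. An assumed range at Week 16.** The documents give no frequency. I assume 0 to about 1% of an arm is missed: 0 to 6 of 585, or 0 to 2 of 195. Planned rates (30% and 10% for IGA; 40% and 15% for EASI75) give 176 and 20, and 234 and 29, responders.

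| Scenario | Difference in points |
|---|---|
| IGA, none missed | 176/585 − 20/195 = 30.09 − 10.26 = 19.83 |
| IGA, 6 missed on tralokinumab | 170/585 − 20/195 = 29.06 − 10.26 = 18.80 |
| IGA, 2 missed on placebo | 176/585 − 18/195 = 30.09 − 9.23 = 20.85 |
| IGA, both | 170/585 − 18/195 = 29.06 − 9.23 = 19.83 |
| EASI75, none missed | 234/585 − 29/195 = 40.00 − 14.87 = 25.13 |
| EASI75, 6 missed on tralokinumab | 228/585 − 29/195 = 38.97 − 14.87 = 24.10 |

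The test used is the unstratified Mantel-Haenszel chi-square, (N−1)(ad−bc)²/(n1·n2·r·(N−r)), where r is the total number of responders. For IGA with 6 reclassified: 779 × (170×175 − 415×20)² / (585×195×190×590) = 28.0, p = 1.2×10⁻⁷ (3.3×10⁻⁸ with none missed). For EASI75 with 6 reclassified, p = 5.7×10⁻¹⁰.

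**Step 6. Maintenance.** The smallest planned difference is Q4W against placebo for IGA, 50% − 5% = 45 points. One case there moves it by 1.4 points (active arm) or 2.9 points (placebo).

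**The case against.** The strongest objection is that no defect is shown. If the codes cover the unlisted agents there is no gap, and the dictionary is not in the documents. That stands, and it is why the point is conditional and the dictionary check is part of the fix.

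A reader might infer that SAP 6.3 contradicts 9.6 and 9.8.2 as well. The documents do not support that. Section 9.6 lists prohibited drugs and 9.8.2 lists reasons to suspend IMP; neither defines rescue, and 9.7 cites 9.8.2 only for the suspension. They matter indirectly. They group Janus kinase inhibitors and biologics with the four drugs named in 9.7, and SAP 6.3 already counts one biologic that 9.7 does not name. Nor does prohibition take a drug out of rescue: TCI, systemic corticosteroids and the four immunosuppressants are prohibited in 9.6 and are rescue in 9.7.

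It can also be said that the SAP, dated 20 May 2019, follows the 11 April 2019 cut-off and precedes unblinding, so the list may already reflect blinded data. The names that go beyond 9.7 fit this. But the SAP does not say so.

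A missed case also needs several things together: a prohibited agent given for atopic dermatitis, no earlier flagged rescue despite the advice to try topical treatment first, an attended visit showing response (missing data count as non-response), and in maintenance no transfer to open-label. This stands and keeps the weight minor.

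Finally, a class term needs clear edges, and it would not catch a listed drug coded to another indication. Both are fair and are reflected in the fix.

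**Conclusion.** The point holds as a minor one. The rule in SAP 6.3 is narrower in wording than the open-ended rescue in protocol 9.7 that the estimand relies on, and no stated rule corrects a missed case. Whether any drug is actually missed depends on the content of the three codes, which the documents do not give.

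A reader might infer that the results are biased towards tralokinumab or that significance is in doubt. Neither is supported. A missed case on tralokinumab inflates the difference, one on placebo shrinks it, and equal shares cancel (19.83 points in both cases above). At planned rates and an assumed 0 to 1% missed, the IGA difference runs from 18.8 to 20.9 points. With 6 tralokinumab subjects reclassified, EASI75 falls from 25.1 to 24.1 points. Both primary endpoints stay far below the 5% level. The maintenance endpoints are more sensitive per case, at 1.1 to 2.9 points, but planned differences there are at least 45 points. The effect is on correct classification and reported rates.

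This rests on the protocol's planned rates and arm sizes, on the assumed 0 to 1% range, and on an unstratified test in place of the stratified one.

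**What to change.** Before unblinding:

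1. Check in the coding dictionary what H02, D07 and D11AH contain. Review a blinded listing of all concomitant medications recorded for atopic dermatitis that fall outside the algorithm. Reason for use is already collected (protocol 9.5). Selecting on the recorded reason, not only on the two coded indication terms, would also show listed drugs coded elsewhere.
2. If the codes already cover these agents, say so in SAP 6.3. Otherwise keep the present codes and names and add to the flag: *or any other systemic immunosuppressive or immunomodulating drug or biologic (other than IMP) given for the same indications*. State whether immunoglobulin and allergen immunotherapy count. Then lock the flag.

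This changes the analysis flag only, not what subjects may receive. The cost is one SAP sentence or clause, one dictionary check and a short listing review, with possibly slightly lower response rates. After unblinding, the same change would look driven by results.

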8.3 Exclusion criteria

- 1. Concurrent enrolment in another clinical trial where the subject is receiving an IMP.
- 2. Previous randomisation in tralokinumab trials.
- 3. Active dermatologic conditions that may confound the diagnosis of AD or would interfere with assessment of treatment, such as scabies, cutaneous lymphoma, or psoriasis.
- 4. Known active allergic or irritant contact dermatitis that is likely to interfere with the assessment of severity of AD.
- 5. Use of tanning beds or phototherapy (narrow band ultraviolet B [NBUVB], ultraviolet B [UVB], ultraviolet A1 [UVA1], psoralen + ultraviolet A [PUVA]), within 6 weeks prior to randomisation.
- 6. Treatment with the following medications within 4 weeks prior to randomisation:
 - Systemic immunosuppressive/immunomodulating drugs (e.g. methotrexate, cyclosporine, azathioprine, mycophenolate mofetil, Janus kinase inhibitors etc.).
 - Systemic corticosteroid use (excludes topical, inhaled, or intranasal delivery).
 - Three or more bleach baths during any week within the 4 weeks.
- 7. Treatment with the following medications within 2 weeks prior to randomisation
 - TCS.
 - TCI.
 - Topical PDE-4 inhibitor.

- 8. Initiation of treatment of AD with prescription emollients or emollients containing additives such as ceramide, hyaluronic acid, urea, or filaggrin degradation products during the screening period (subjects may continue using stable doses of such emollients if initiated before the screening visit).
- 9. Receipt of live attenuated vaccines 30 days prior to the date of randomisation and during the trial including the safety follow-up period.
 - Receipt of inactive/killed vaccinations (e.g. inactive influenza) are allowed, provided they are not administered within 5 days before/after any study visit.
- 10. Receipt of any marketed (i.e. immunoglobulin, anti-IgE) or investigational biologic agent, including dupilumab:
 - Any cell-depleting agents including but not limited to rituximab: within 6 months prior to randomisation, or until lymphocyte count returns to normal, whichever is longer.
 - Other biologics: within 3 months or 5 half-lives, whichever is longer, prior to randomisation.
 - 11. Receipt of any investigational non-biologic agent within 5 half-lives prior to randomisation.
 - 12. Receipt of blood products within 4 weeks prior to screening.
 - 13. Major surgery within 8 weeks prior to screening, or planned in-patient surgery or hospitalisation during the trial period.

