9.5 Concomitant medication and procedures

Any medication or vaccine that the subject receives from 3 months prior to screening through safety follow-up (FU1 [Week 66] or FU2 [Week 82]) must be recorded in the subject's medical record and the eCRF along with details such as:

- Reason for use.
- Dates of administration including start and stop dates.
- Dosage information including dose and frequency.
- For topical treatments: size of treated area ($\leq 250 \text{ cm} 2 \text{ or } > 250 \text{ cm} 2$).

Similarly, concomitant procedures (including body location, diagnosis, and start and stop date) must also be recorded in the subject's medical record and the eCRF. Note: in this trial, only surgical procedures will be recorded.

Investigators may prescribe concomitant medications or treatments to provide adequate supportive care as deemed necessary, except for medications listed in Section 9.6. The

Trial ID: LP0162-1325	Date: 14-Aug-2018	Version: 4.0
		Page 58 of 169

sponsor's medical expert should be contacted if there are any questions regarding concomitant or prior therapy.

Concomitant medication for conditions other than AD may be continued throughout the trial without any change in dosage whenever possible.

The following concomitant medications related to AD treatment are permitted from screening through safety follow-up (FU1 [Week 66] or FU2 [Week 82]):

- Oral antibiotics, antiviral, or antifungal therapy for skin infections as appropriate.
- Stable doses of an emollient (see Section 9.4 for allowed emollients; subjects must apply such emollients twice daily [or more, as needed] for at least 14 days before baseline and throughout trial participation).
- Oral anti-histamines.

In addition, the use of topical treatments is permitted during safety follow-up (from Week 52 or Week 68) at the investigator's discretion.

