#### Concomitant medication

For incomplete start dates of concomitant medication, the following rules apply:

• If a medication start day is missing, but start month and year is not missing, it will be assumed that the start day is the first day of the month. If the medication start day and month is missing, but start year is not missing, it will be assumed that the start day is

01 January. If the medication start day, month and year is missing, it will be assumed that the medication was started before study start, and the date will appear as missing in the data.

For incomplete end dates of concomitant medication, the following rules apply:

• If a medication end day is missing, but end month and year is not missing, it will be assumed that the end day is the last day of the month. If the medication end day and month is missing, but end year is not missing, it will be assumed that the end day was 31 December. If the medication end day, month and year is missing, it will be assumed that the medication was ongoing at the end of the study, and the date will appear as missing in the data.

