#### Concomitant medication

For the purpose of associating concomitant medication with trial periods, the convention will be that the start time of day of concomitant medications is 23:59:59, and end time is 00:00:00, unless the start day is equal to the end day in which case both start and end time will be assumed to be 23:59:59. As a consequence, rescue medication starting on the day of transfer between two periods will be associated with the latter period only, and rescue medication ending on the day of transfer between two periods will be associated with the start period only is equal to the end day).

Unlike adverse events which are assigned to a single period based on their start date only, a concomitant medication can be associated with more than one period.

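### Incomplete stop dates are imputed forward past the first dose, so correctly washed-out AD drugs can be listed as rescue, and the plan does not clearly keep that flag out of the efficacy analyses

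*SAP*

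**What the plan says.** Protocol 9.5 requires recording of "Any medication or vaccine that the subject receives from 3 months prior to screening through safety follow-up", so AD drugs washed out before randomisation sit in the same data as on-treatment medication. Protocol 8.3 excludes subjects for "Treatment with the following medications within 2 weeks prior to randomisation" (TCS, TCI, topical PDE-4 inhibitors) and sets 4 weeks for systemic immunosuppressants and corticosteroids.

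SAP 6.3: "Rescue medication is defined by the following algorithm: Concomitant medications with Dermatitis atopic or Dermatitis infected as the preferred term for the indication", combined with a list of ATC codes and named drugs. The definition has no start-date condition. The initial-period rescue table "will include rescue medication taken (but not necessarily initiated) between the first dose of initial treatment" and the first maintenance or open-label dose. The maintenance table uses the same prevalent-use wording.

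SAP 6.8.3, for incomplete stop dates: with the day missing, "it will be assumed that the end day is the last day of the month"; with day and month missing, 31 December; with everything missing, "it will be assumed that the medication was ongoing at the end of the study". SAP 6.8.4 works by overlap: "a concomitant medication can be associated with more than one period".

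Protocol 12.3.5.1 names the *initiation* of rescue as the intercurrent event, and 12.3.5.1.1 defines response in the same terms. The analysis rule in 12.3.5.1.1 is worded differently: "Subjects who prior to the Week 16 visit have received rescue medication will be considered non-responders". Protocol 12.3.6.1 uses the *have received* form for Week 52, and SAP 6.6.3 does so for the composite estimand of the continuous endpoints.

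**The concern.** Read together, these rules let a drug that was properly stopped before randomisation acquire an imputed stop date after the first dose, match the rescue algorithm, and enter the on-treatment rescue table. Nothing in SAP 6.8.3 uses the washout already confirmed at eligibility. The adverse-event rules in the same section at least use a complete end date before exposure start to rule an event out. The table of concomitant medication at baseline (SAP 6.1) relies on the same date rules and is exposed in the same way.

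The larger stake is whether the same flag drives efficacy. No section says whether a drug started before the first dose sets the non-responder flag. If it did, an affected subject would:
- be a non-responder for IGA 0/1, EASI75 and the pruritus endpoint;
- leave the Week 52 populations, which require Week 16 response without rescue (Protocol 12.3.6.1);
- have no usable post-baseline SCORAD or DLQI data, so that SAP 6.6.3 would enter a change of 0 at the first post-baseline visit.

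**Working it through.** **1. The plan's own figure.** Protocol 12.1 gives 585:195 subjects, IGA 0/1 30% v 10%, EASI75 40% v 15%, two-sided 5%, and power above 99% for both. Power = Φ[(d − 1.96·SE0)/SE1], with SE0 pooled and SE1 unpooled.
- IGA: SE0 = √(0.25·0.75·(1/585 + 1/195)) = 0.0358; SE1 = √(0.21/585 + 0.09/195) = 0.0286; power 0.999997.
- EASI75: power 0.99999995.

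Both stated figures are reproduced.

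**2. When the imputed stop passes the first dose.** Let the drug stop w days before the first dose. First-dose dates are assumed uniform over a 365-day year, and randomisation is taken as the day of first dose. SAP 6.8.4 sets the end time at 00:00:00, so an imputed stop on the first-dose day itself does not count.
- *Day missing:* the stop must lie in the first-dose month and the first dose must not be on the last day of that month. A month of L days contributes max(0, L − w − 1) dates.
- *Day and month missing:* same calendar year and not 31 December, so (365 − w − 1)/365.
- *Whole date missing:* always.

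| w (days) | Day missing | Day and month missing |
|---|---|---|
| 14 | (7·16 + 4·15 + 13)/365 = 185/365 = 51% | 350/365 = 96% |
| 21 | (7·9 + 4·8 + 6)/365 = 101/365 = 28% | 343/365 = 94% |
| 28 | (7·2 + 4·1)/365 = 18/365 = 5% | 336/365 = 92% |
| 30 | 0% | 334/365 = 92% |
| 90 | 0% | 274/365 = 75% |

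**3. Effect if the flag were reused for efficacy.** Let q be the share of subjects wrongly flagged. The documents do not give q, so the values below are assumptions. The drug use predates randomisation, so q is taken as equal in both arms and, for simplicity, unrelated to response. Each response rate is multiplied by (1 − q).

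| q | IGA difference (points) | EASI75 difference (points) | Tralokinumab IGA responders, 585·0.30·(1 − q) |
|---|---|---|---|
| 0 | 20.0 | 25.0 | 175.5 |
| 1% | 19.8 | 24.75 | 173.7 |
| 5% | 19.0 | 23.75 | 166.7 |
| 10% | 18.0 | 22.5 | 158.0 |
| 30% | 14.0 | 17.5 | 122.9 |

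At q = 5%, about 9 tralokinumab and 1 placebo IGA responders are lost (585·0.30·0.05 = 8.8; 195·0.10·0.05 = 1.0). At q = 30%, an extreme case, power is still 99.92% for IGA and 99.99% for EASI75.

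**4. Wording side by side.** *Initiation* appears in the event definition, the definition of response, and the data-exclusion rules for the hypothetical estimand. *Have received* appears in the non-responder rules for Week 16 and Week 52. The SAP's only rule for placing rescue medication in a trial period is overlap.

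**The case against.** The strongest reply is that the SAP 6.3 sentence governs a descriptive table, and the overlap rule in 6.8.4 is limited to associating medication with periods. The protocol's efficacy event is initiation, and the SAP says efficacy follows the protocol. The one SAP 6.3 sentence linking rescue to efficacy assessments is keyed to the start date. Protocol 9.7 describes rescue as treatment given during the period to control intolerable symptoms. On that reading stop-date imputation never touches an endpoint. This stands to an important degree: a reader might infer that the plan turns washed-out responders into non-responders, and the documents do not say so. What remains is that the operative analysis rule is worded on receipt, and nothing tells the programmer which wording governs a drug started before the first dose.

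A reader might also infer that every incomplete stop date is affected. That is not so. With only the day missing, stops in an earlier calendar month are harmless, and for systemic agents with a 4-week washout the share is at most about 5%. Stops 14-28 days before first dose fall within screening, stop dates are required data, and discrepant entries are queried, so such records may be few. A blank stop date may also simply mean that the drug is ongoing.

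Treating an unknown stop as continued use is a cautious default, since it catches undeclared continuation. That is a fair reason to keep it as a sensitivity analysis. Finally, the treatment-policy estimand ignores rescue and is untouched.

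**Conclusion.** The concern holds in a limited form. Applied as written, the SAP will list a correctly washed-out AD drug as initial-period rescue whenever its stop date is incomplete and the imputed date passes the first dose. That is a defect in the rescue tables. For the confirmatory endpoints it is an unresolved ambiguity with a possible consequence, which occurs only if the table flag is reused.

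The size cannot be fixed from the documents because q is not given. At an assumed 1-5%, the IGA difference would move from 20 to 19.8-19.0 points and EASI75 from 25 to 24.75-23.75. The error would be non-differential and toward no difference. It would not inflate type I error, and primary power would stay above 99%. A reader should not infer a threat to the primary conclusion. The possible harm is understated effects, inflated rescue counts and smaller Week 52 populations.

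**What to change.** 1. **SAP 6.3:** state that, for all estimands and all rescue tables, the rescue event is a qualifying drug with a start date on or after the first dose, or one documented as used after it. The second clause is needed because SAP 6.8.3 moves incomplete start dates backward, so a start-date rule alone could miss true rescue.
2. **SAP 6.8.3:** do not impute the stop date of a drug started before the first dose past the first dose, unless the record is marked ongoing or later use is documented.
3. Before unblinding, query the incomplete stop dates of drugs that match the algorithm, and list the affected subjects blinded.
4. Keep the current rule as a sensitivity analysis.

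The cost is two SAP sentences, one derivation change and a blinded listing. The drawback is that an undocumented washout violator may no longer be flagged; the sensitivity analysis under the current rule covers this.
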